7.3 Sample management

All trial milk powder for the study will be provided to the subjects free of charge. The trial and control powder were stored in the central warehouse and distributed by the investigator by subject number and trial protocol.

8 Outcome indicators

8.1 Main end point

Intestinal indicators (16S rRNA, SCFAs).

8.2 Secondary end point

Inflammation index: serum hsCRP; nutritional index: serum albumin; growth and development index: height, weight, head circumference, chest circumference; immune index: fecal sIgA, blood lymphocyte subgroup; bone development index: osteocalcin, alkaline phosphatase; tolerance index: survey of infant gastrointestinal comfort, infant sleep crying, infant diarrhea and upper respiratory tract infection, infant stool Bristol stool classification; cognitive development index: Bailey Infant Development Scale (IV edition), serum amino acids.

8.3 Safety evaluation index

Adverse events, serious adverse events.

9 Data statistics method

9.1 Data analysis software

Demographic, safety and efficacy data were analyzed using the SAS (version 9.4) software.

9.2 General data analysis

Statistical description is mainly used, and statistical inference is used for reference only. Quantitative data were expressed by n (number of subjects with non-missing values), mean, median, standard deviation, maximum value, and minimum value, and qualitative data were expressed by frequency and percentage.

The missing values in the statistical analysis involved in this statistical analysis plan will not be inserted. Outliers are determined in a unified discussion before the database lock library.

9.3 Analyze the crowd

The Statistical analysis population data sets were defined as follows:

Screening Set (Screening Set): includes all subjects who signed the informed consent and participated in trial screening.

Full Analysis Set (Full Analysis Set, FAS): All subjects who participated in the trial and completed at least Visit 1. The FAS set is the main population for the efficacy analysis.

Compliance Set (Per-Protocol set, PPS): is a subset of the full analysis set containing subjects who completed all visits to the trial and had no major protocol deviations during the trial. The PPS set is a secondary population for the efficacy analysis.

Safety Analysis Set (Safety Set, SS): The Safety Analysis Set includes all subjects who participated and received test samples with records of safety indicators.

9.4 Subject completion status

To clarify the implementation of the clinical trial and the status of the clinical

trial analysis set, a clear summary of the subjects from the completion of the clinical trial, including the following:

(1) Subject Clinical Trial Completion Form, including

- Number of screened subjects;
- Number of unlisted subjects;
- Number of randomized subjects;

- Number and percentage of subjects who have completed the clinical trial;

- Number and percentage of subjects withdrawing early from the clinical trial;

- And to distinguish the number and percentage of subjects withdrawing early from the clinical trial for different reasons.

(2) Number and percentages of the different analysis sets.

(3) Protocol deviation summary.

(4) Subject completion in the clinical trial and the analysis set are provided in a list form.

9.5 Demographic data

Subject demographic data will be summarized according to the full analysis set. The summary of demographic data should include the following: (1) age (age year) - the difference between the date of signed informed consent and the date of birth / 365.25; (2) gender- -male / female; (3) ethnic group- -Han / other.

9.6 adverse event

All reported adverse event names and terminologies need to be coded in the latest version of the MedDRA. For all adverse event tables, subjects were counted only once in each preferred term (Preferred Term, PT) and systemic organoids (System Organ Class, SOC). Unless specifically defined, adverse events were ranked in descending order of the preferred term frequency in each system organ class. If several preferred terms in the same system organclass have the same frequency, then in the literal order of preferred terms.

All adverse events will be summarized by SOC, PT and CTCAE criteria, including

• Number of subjects, percentage of adverse events, and number of adverse events

• Number and percentage of subjects with serious adverse events and number of adverse events

• Number of subjects with early withdrawal due to adverse events and number of adverse events

All adverse events will be displayed as lists.

9.7 efficiency analysis

9.7.1 Main endpoint indicators

Primary endpoint index: Changes in the intestinal flora of infants compared between the test group and the control group.

9.7.2 statistical analysis technique

16 The lowest ranked taxon O TUs was obtained from sequencing data for further analysis.

(1) Analysis of the bacterial species diversity profile

• The diluability curve (Rarefaction curve) is used to analyze whether the existing OTU data can reflect the diversity of the sample flora, and the sequencing depth is used to evaluate whether the sequencing data amount of the sample is reasonable. Random sampling of sequences is used to construct the number of sequences drawn and the number of OTU they can represent. When the curve is flat, it indicates that the amount of sequencing data is reasonable.

• Species composition analysis was conducted, and according to the species information and abundance information of O TUs, the appropriate taxonomic level (species <genus <family <order <class <phyla) was selected to draw the colony columns of different groups of samples.

• The Alpha Diversity (Alpha diversity) index was used to quantify the bacterial community characteristics of the samples, as described by the S obs, C hao, Ace, Shannon, and S impson index. The S obs Index, Chao, index and Ace index can estimate the number of species in the sample, and the Shannon index and S impson index reflect the species richness and species uniformity of the sample.

(2) Analysis of microflora composition differences among samples

• Differences in species composition between different groups were analyzed using W ilcoxon (comparing two groups) and K ruskal-Wallis (three groups and above) to compare differences in Alpha diversity index between groups, if P < 0.05.

• Beta diversity (Beta diversity) analysis was used to use the species composition or evolutionary relationship between species and abundance information to calculate the inter-sample distance, and the similarity or difference of community composition between different grouped samples was explored. The results are shown in Heatmap diagram.

• Using p rincipal component analysis (p rincipal component analysis, PCA) to assess whether infant samples from different groups can be distinguished. When the sample composition is more similar, the closer the distance reflected in the PCA plot is. Samples from different backgrounds may exhibit a distribution of dispersion and aggregation.

• Using W ilcoxon and K ruskal-Wallis tests by LEfSe software to identify significantly different species between groups and visually show the distribution of different species between groups at each taxonomic level.

(3) Association analysis of environmental factors

• Correlation analysis was used to explore the associations between infant gut microbiota and environmental factors (sex, birth weight, etc.) in different groups. Correlation coefficients were calculated using P earson and S pearman when samples cannot satisfy a continuous normal distribution and a linear relationship. The results are presented as the Heatmap plots.

10 Management plan for common / serious adverse events

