11.1 Protection of subject privacy	

	11.2 informed consent	.37
	11.3 Approval of the ethics committee	. 37
	11.4 Declaration of Helsinki	. 38
12	Quality control and quality assurance	.38
13	Study termination	38

1 Summary of the clinical trial protocol

Research name	Effect of adding breast milk oligosaccharides and multinutrient optimized infant formula on the growth and development of infants aged 0 to 1 years: a multicenter, double-blind, randomized, controlled trial			
research design	Multicenter, randomized, controlled, parallel, double-blind trial			
sample capacity	240			
Interventio n cycle	360 Days			
purpose of research	Compare add milk oligosaccharides and a variety of nutrients optimization of infant formula and conventional infant formula on the immune function of infants under 1 year of age, and compared with breastfeeding infants, explore different infant formula on infant intestinal health, immune function, growth and development, cognitive development and tolerance.			
Main end point	Intestinal indicators (16s r RNA, SCFAs)			
Secondary end point	 Inflammation indicators: serum hsCRP; Nutritional index: serum albumin; Immune indicators: fecal sIgA and blood lymphocyte subsets; Growth and development indicators: height, weight, head circumference and chest circumference; Bone development indicators: osteocalcin, alkaline phosphatase; Tolerance indicators: survey of infant gastrointestinal comfort, infant sleep crying, infant diarrhea and upper respiratory tract infection, infant stool Bristol stool classification; Cognitive development: Bailey Infant Development Scale (version 			

	IV), serum amino acids.					
Safety indicators	• Adverse events and serious adverse events.					
	Inclusion criteria for the breast-feeding group:					
	\cdot The 0 ~ 28 days after birth;					
	· Single-child birth;					
	• The gestational age was from 37 to 42 weeks;					
	\cdot Birth weight is 2500 ~ 4000 g;					
	• Parents or guardians agree to exclude the infant from participating in other interventional clinical studies during this study;					
	• Parents or guardians agreed to feed the baby according to the trial protocol;					
Inclusion	Inclusion criteria for the artificial feeding group:					
criteria	\cdot The 0 ~ 28 days after birth;					
	· Single-child birth;					
	• The gestational age was from 37 to 42 weeks;					
	\cdot Birth weight is 2500 ~ 4000 g;					

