6.5.2 Sample size and calculation basis

 J57 The study enrolled 88 test group, 87 control infants, 34 breastfed infants with 1g / L 2 ' / FL and 0.5 g / L LNnT to formula-fed infants, control formula-fed infants and breast-fed infants. All the fecal samples available at 3 months of age were 58 in the test group, 65 in the control group, and 34 in the breastfeeding group. They evaluated the microbiota using 16S rRNA gene sequencing and metagenomics, and found that the microbiota composition of the test group was different from that of the control group and closer to that of the breastfeeding group. In this study, the experimental group, control group and breastfeeding group are planned to include 80 subjects, calculated by the shedding rate (failure rate) of 20%. The effective sample size of each group is expected to be 64 cases, which can meet the study needs.

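### The main endpoint includes SCFAs in Sections 1 and 8.1 but is flora only in 9.7.1; in addition, a 9.7.2 bullet announced as a species-composition test actually tests alpha diversity

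*Protocol*

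**What the plan says.** The main endpoint is stated in three places in the protocol.

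- Section 1 (summary table): "Intestinal indicators (16s r RNA, SCFAs", with the bracket closing after SCFAs.
- Section 8.1: "Intestinal indicators (16S rRNA, SCFAs", the same two components.
- Section 9.7.1: "Primary endpoint index: Changes in the intestinal flora of infants compared between the test group and the control group".

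Sections 6.6.1, 6.6.3 and 6.6.4 schedule stool SCFAs at Visits 1, 3 and 4. Section 9.7.2 then works only from sequencing-derived OTUs. Its part (2), on differences in microflora composition, has four elements:

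- A rank test, introduced as "Differences in species composition between different groups were analyzed using W ilcoxon (comparing two groups" (with Kruskal-Wallis for three or more groups), whose object is given later in the same sentence: "to compare differences in Alpha diversity index between groups, if P < 0.05".
- Beta-diversity distances, for which "The results are shown in Heatmap diagram".
- PCA, read from a plot.
- LEfSe: "Using W ilcoxon and K ruskal-Wallis tests by LEfSe software to identify significantly different species between groups".

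Section 9.2 says that description is the main method and that inference is for reference only. Section 4 calls the trial exploratory.

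**The concern.** SCFAs are metabolites. Section 2.1 itself describes them as fermentation products of gut bacteria, so the word flora in 9.7.1 does not cover them. The protocol thus carries two incompatible definitions of its main endpoint, and the analysis section follows the narrower one without saying that the other has been given up. Anyone reporting the trial could call SCFAs primary by citing 8.1, or not primary by citing 9.7.1.

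The second matter is narrower. Alpha-diversity indices describe how many species a sample holds and how evenly they are spread, as 9.7.2(1) itself explains. They do not say which species are present. A P-value from them, reported under the label of species composition, would be a diversity result presented as a composition result.

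**Working it through.** **Endpoint definition.** No arithmetic applies, so the passages are set side by side.

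| Place | 16S rRNA / flora | SCFAs |
|---|---|---|
| Section 1, main end point | yes | yes |
| Section 8.1 | yes | yes |
| Section 9.7.1 | yes | not named |
| Sections 9.1 to 9.7.2, analysis text | yes | not named |

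SCFAs are in 2 of 3 definitions and are mentioned 0 times in Section 9. The only rule there that reaches them is 9.2, which summarises any quantitative variable by n, mean, median, SD and range. That rule neither compares arms nor says whether SCFAs are primary.

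**The 9.7.2(2) bullet.** Each element is matched to the question it answers.

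| Element | Question answered | Between-group test stated? |
|---|---|---|
| Wilcoxon / Kruskal-Wallis on alpha indices | Do richness or evenness differ? | yes |
| Beta diversity | Do whole communities differ? | no, heatmap |
| PCA | Do whole communities separate? | no, plot |
| LEfSe | Which single taxa differ? | yes, taxon by taxon |

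The one row that concerns the whole community and could carry a test (beta diversity) has none.

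**Does the label matter in practice?** The following is an illustration only. The documents give no taxon counts, abundances or variability, so these are assumed: 60 taxa with a long tail, Dirichlet-multinomial concentration 10, 20 or 50, depth 5000. The arm size is the protocol's own: 80 × (1 − 0.20) = 64, which reproduces Section 6.5.2. Alpha indices are compared by Wilcoxon at 0.05. PERMANOVA uses Bray-Curtis distances with 199 permutations. Entries are rejection rates.

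| Scenario | Alpha indices | PERMANOVA |
|---|---|---|
| No difference | 3–8% | 3–6% |
| Leading taxon 21% to 31%, all others shrink in proportion | 58–100% | 97–100% |
| Taxa at 17.7% and 6.6% exchange places | 4–6% | 100% |
| One taxon up 10 points, two-thirds from a 20% taxon and one-third from a 10% taxon | Sobs, Chao, Ace 2–9%; Shannon, Simpson 5–100% | 99–100% |

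The last row is the kind of pattern described in Section 2.1 (more bifidobacterium, less of two other groups). Shannon and Simpson depend heavily on the starting level of the rising taxon: 12–59% from 5%, 5–11% from 10%, 25–100% from 20% and 59–100% from 40%. The mean Shannon difference even changes sign, from +0.03 (5% to 15%) to −0.06 (20% to 30%). So alpha diversity is not blind to composition, but it is not a measure of it.

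In the same last-row scenario, a per-taxon Wilcoxon at 0.05 (the test inside LEfSe, without its effect-size filter) finds the rising taxon in 93–100% of trials and each falling taxon in 71–100%. With Bonferroni over 60 taxa, at least one of the three is found in 79–100%.

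**The case against.** The strongest reply is that only the protocol is at hand, that an SCFA test and its visit belong in an analysis plan, and that 9.2 makes description the rule for everything in a trial called exploratory. That reply stands as far as the absence of a detailed SCFA test goes. It does not answer the contradiction: an analysis plan would still inherit two definitions of the main endpoint, and an exploratory trial that declares one still needs it stated once.

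On the bullet, one can fairly say that the text is a rough translation and that the same sentence names the alpha-diversity index, so a careful reader knows what is tested. This stands in part, and it is why the point is secondary.

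Three stronger readings are tempting, and the documents do not support them.

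- A reader might infer that the plan would miss the expected shift in flora. It would not: LEfSe is in the plan and, under the assumptions above, detects the rising taxon in 93–100% of trials.
- A reader might infer that leaving SCFA status open raises a 5% false-positive rate by a calculable amount. The protocol has no single 5% primary test to start from. Five alpha indices are compared at P < 0.05, and four of them at one visit already give some P below 0.05 in 10–14% of simulated trials with no difference.
- A reader might infer that Section 6.5.2 bases the sample size on an overall test of composition. It reports only that in a cited study "the microbiota composition of the test group was different from that of the control group". It names no overall test and gives no power calculation.

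**Conclusion.** The endpoint contradiction holds on the text alone and needs no assumption: two definitions include SCFAs, one does not, and the analysis section never mentions them. It should be corrected. The documents do not show which version is intended.

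The second point holds as a mislabelled bullet together with an unstated overall comparison of composition. Its consequence is limited, because single taxa are tested by LEfSe, the trial is exploratory, and inference is for reference only. The simulated rates rest on assumed abundances and variability. They show only that an alpha-diversity P-value should not be reported as a composition result; they are not an estimate of this trial's power.

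**What to change.** 1. Before any data are seen, make Sections 1, 8.1 and 9.7.1 give the same main endpoint. Either keep SCFAs as primary, name them in 9.7.1 and add to 9.7.2 a randomised test-versus-control comparison at a named visit, or move them to the secondary endpoints in 8.2.
2. Reword the first bullet of 9.7.2(2) as a comparison of alpha diversity between groups.
3. Add a permutation test of test versus control (for example PERMANOVA, with a check of dispersion) on the beta-diversity distances that the plan already calculates. Keep alpha diversity and LEfSe as supportive.

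The cost is protocol wording and a few lines of analysis on data already scheduled for collection. PERMANOVA gives no direction and can be slightly weaker than Shannon for a small diffuse rise: 43% against 52% for a leading taxon going from 21% to 26% in the most variable setting simulated. That is a reason to keep the supportive analyses beside it.

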3.4 Bifidobacterium long long subspecies BB536

Bifidobacterium BB536 isolated the intestines of healthy infants in 1969 and has been approved for infant food in Japan and the United States. It is the first affinity human Bifidobacterium strain (HRB) recognized by the US FDA. At the same time, in 2022, it was approved to be included in China's list of edible fungus list.

As of March 2022, more than 220 academic papers were published based on BB536. A number of clinical studies on infants at home and abroad have proved that the strain has good food safety. Studies have proved that BB536 is effective in maintaining intestinal health, improving immunity, and preventing infection.

3 Study purpose and significance

To compare the effects of breast milk oligosaccharide and multinutrientoptimized infant formula and conventional infant formula on the intestinal health of infants under 1 year of age. In comparison with breast-fed infants, the effects of different infant formulas on infant growth and development, cognitive development, immune function, intestinal comfort, crying, and upper respiratory tract infection were explored.

4 research contents

This trial is a multicenter, randomized, controlled, parallel, double-blind, exploratory trial to compare the effects of infant formula, conventional infant formula on infant formula and breast milk in early life.

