240 subjects are expected to be required for this trial. From 0 to 28 days after birth, infants who had signed informed consent by a guardian were screened. Guardian according to their own will choose to attend breastfeeding group or artificial feeding group (mother for subjective and objective reasons for exclusive breastfeeding, can choose to join artificial feeding group, the researchers shall not interfere in the decision of the guardian or guide), breast feeding group and artificial feeding group subjects of 80 cases and 160 cases, respectively.160 subjects in the artificial feeding group were randomly assigned to the experimental group and the control group in a ratio of 1:1 ratio. The experimental formula and control formula were used for artificial feeding or mixed feeding. Artificial feeding was conducted no less than 2 times a day at 0 to 4 months and no less than 5 times a day at 4 to 12 months. Infants in the breastfeeding group need to be breastfed or mixed fed, exclusively breastfeeding daily at 0 to 4 months of age (must be fully breastfed 1 day before the visit), and breastfeeding at least once a day at 4 to 12 months of age.

From the perspective of ethical and subject protection, if the infant and guardian

are eligible and willing to breastfeeding, we will assign the subject to the breastfed group, rather than against the wishes of the parent. If the parent / legal guardian is unable to breastfeed exclusively for objective reasons, or clearly and strongly willing not to breast, these infants will be randomized to the trial or the control group. It should be noted that during the decision-making process, the investigator should encourage the parents / guardian to breastfeeding the infant; rather than interfering or guiding the decision-making process to induce the test infant to participate in the artificial feeding group.

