6.1 Test flow chart

6.2 recruit

The investigator will identify suitable infants, contact their parents or guardians by telephone and otherwise, and make an appointment for informed consent and subject screening.

6.3 informed consent

The subject's guardian must personally sign the informed consent form and date before conducting any trial process. If the version is updated, contact the guardian to sign the latest version of the informed consent.

A written version of the informed consent was provided to the guardian of the subject, and the investigator should explain the following: the nature of the trial; the content of the subject; the requirements of the protocol; known side effects and any risks involved in participation. The guardian should also be clearly informed that the baby can be withdrawn from the study at any time for any reason, without affecting the baby's medical treatment, legal rights, and no obligation to provide a reason for the withdrawal.

The guardian of the subject was allowed enough time to consider the relevant information and the opportunity to ask the researcher, their GP or other independent party to decide whether to enroll the infant in the trial. The subject's guardian will then sign and date the informed consent form, followed by the investigator giving the informed consent. The investigator who gave the informed consent must have the appropriate qualifications and experience and must be authorized by the principal investigator at each institution. A copy of the signed informed consent form will be given to the subject's guardian for retention and the original remains at the study institution.

6.4 dressing by screening

The investigator will ask the guardian, investigate the basic information of the subject infant, fill in the screening record and the Subject Screening and Enrollment Registration Form, and the infant will be included in the study after meeting the inclusion and exclusion criteria. If the guardian chooses to exclusively breastfeed the infant, the infant will be assigned to the breastfeeding group; if due chooses artificial or mixed feeding, the infant will be randomized to the trial or control group.

6.5 randomization

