6.6 Interview

6.6.1 Visit 1

Visit 1 will be performed on the 28th day of life and the investigator will obtain the following information:

· Mode of delivery;

· Pregnancy-related complications;

· Parents' physical condition (height, weight, medical history);

· Parents' living habits (smoking history, drinking history, exercise habits);

· Parents' social and economic background (education level, employment status);

· Growth and development parameters (height, head circumference, chest circumference, body weight);

- Stool samples (16S rRNA, SCFAs, sIgA);
- · Gastrointestinal comfort survey and questionnaire;
- · Questionnaire on baby crying condition;
- · Questionnaire on infant diarrhea;
- · Questionnaire on upper respiratory tract infection in infants;

⁵⁷Steenhout P, Sperisen P, Martin F, et al.Term Infant Formula Supplemented with Human Milk Oligosaccharides (2' Fucosyllactose and Lacto - N - neotetraose) Shifts Stool Microbiota and Metabolic Signatures Closer to that of Breastfed Infants[J].The FASEB Journal, 2016, 30.

- · The Bristol Stool Classification Questionnaire;
- · Past medical history and current medical history.

6.6.2 Visit 2

Visit 2 will be conducted on Birth Day 90 with a window of 3 days and the investigator will measure and obtain the following information:

· Growth and development parameters (height, head circumference, chest circumference, body weight);

- · Gastrointestinal comfort survey and questionnaire;
- · Questionnaire on baby crying condition;
- · Questionnaire on infant diarrhea;
- · Questionnaire on upper respiratory tract infection in infants;
- · The Bristol Stool Classification Questionnaire;
- · Adverse events and serious adverse events.

6.6.3 Visit 3

Visit 3 will be conducted on Post Birth Day 180 with a window of 5 days and the investigator will measure and obtain the following information:

· Growth and development parameters (height, head circumference, chest circumference, body weight);

- Blood samples (hsCRP, analysis of lymphocyte subsets, amino acids, osteocalcin, alkaline phosphatase, albumin);
- Stool samples (16S rRNA, SCFAs, sIgA);
- · Gastrointestinal comfort survey and questionnaire;
- · Questionnaire on baby crying condition;
- · Questionnaire on infant diarrhea;
- · Questionnaire on upper respiratory tract infection in infants;
- · The Bristol Stool Classification Questionnaire;
- · Adverse events and serious adverse events.

6.6.4 Visit 4

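### Flora comparisons with the self-selected breastfed group are planned as unadjusted rank tests, although the likely confounders are recorded and could be used for adjustment

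*Protocol*

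**What the plan says.** Two kinds of group formation sit side by side in the protocol. Section 4 randomises the formula-fed infants: "160 subjects in the artificial feeding group were randomly assigned to the experimental group and the control group in a ratio of 1:1 ratio". The third group is not randomised. Section 4 states "Guardian according to their own will choose to attend breastfeeding group or artificial feeding group", and section 6.4 repeats the rule at screening: "If the guardian chooses to exclusively breastfeed the infant, the infant will be assigned to the breastfeeding group".

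The breastfed group has a purpose beyond description. Section 3 frames part of the objective around it: "In comparison with breast-fed infants, the effects of different infant formulas on infant growth and development, cognitive development, immune function" and further outcomes are to be explored.

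For the flora, section 9.7.2 names the tests. Alpha diversity indices are compared by Wilcoxon and Kruskal-Wallis ("comparing two groups) and K ruskal-Wallis (three groups and above") with a threshold of P < 0.05, and taxa are compared with the same two "tests by LEfSe software to identify significantly different species between groups". Beta diversity is shown as a heatmap and PCA as a plot.

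Section 6.6.1 collects background factors at Visit 1, among them mode of delivery, pregnancy complications and "Parents' social and economic background (education level, employment status"). The only analysis in 9.7.2 that uses such factors is a correlation of "associations between infant gut microbiota and environmental factors (sex, birth weight, etc.) in different groups", again shown as a heatmap. The demographic summary in 9.5 lists age, gender and ethnic group only.

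**The concern.** Mothers who breastfeed exclusively and mothers who cannot or do not wish to do so may differ in how they delivered and in family circumstances. Section 6.5.1 also has centres recruiting competitively, so the mix of breastfed and formula-fed infants can differ by centre. Any of these factors that also relates to the infant flora becomes part of the observed formula-versus-breastfed difference.

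A rank test without covariates cannot separate these parts. A correlation of flora with background factors does not adjust a group difference. Because the demographic table omits delivery mode and family background, a reader would not even see whether the groups were imbalanced on them.

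At stake is the interpretation of flora differences between formula-fed and breastfed infants, which is what the third group was added to inform.

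**Working it through.** **The plan's own figures.** Section 6.5.2 plans 80 infants per group with 20% loss: 80 × (1 − 0.20) = 64 evaluable per group, and 3 × 80 = 240 in total. Both reproduce. The section gives no effect size, SD or power.

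**Which comparisons are exposed.**

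- Test versus control: randomised 1:1 (section 4) and the primary contrast (9.7.1). Not exposed.
- Formula versus breastfed, flora: formed by choice, tests fixed in 9.7.2 without covariates. Exposed.
- Three-group Kruskal-Wallis: includes the breastfed group. Exposed, and a significant result does not show which groups differ.
- Secondary endpoints (8.2): 9.7.2 names no test for them, so there is no fixed unadjusted method to criticise.

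**Size.** The documents give neither the imbalance in any factor nor its effect on flora, so everything below is assumption. For one binary factor on an outcome with SD 1:

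bias = (difference in share between groups) × (effect of the factor in SD)

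A 20-point difference and a 0.5 SD effect give 0.20 × 0.5 = 0.10 SD. With 64 per group the standard error of a mean difference is √(2/64) = 0.177 SD, so the 95% CI half-width is 1.96 × 0.177 = 0.35 SD. A bias of 0.10 SD is 0.10 / 0.177 = 0.57 standard errors: modest beside the sampling error of one comparison, but it does not shrink with more infants.

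**Range and mechanism.** A simulation used 3,000 runs per row and effect size, 64 per group, normal outcome with SD 1, no true feeding effect, one binary factor and a two-sided 5% level (the protocol does not state sidedness). Entries are for factor effects of 0.3 / 0.5 / 0.8 SD; the last four columns are rejection rates in %.

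| Share with factor, breastfed vs formula | Bias (SD) | Wilcoxon, formula vs breastfed | Kruskal-Wallis, three groups | Formula vs breastfed, adjusted | Wilcoxon, test vs control |
|---|---|---|---|---|---|
| 40% vs 50% | 0.03 / 0.05 / 0.08 | 4.8 / 5.1 / 6.6 | 5.2 / 5.1 / 6.6 | 4.6 / 4.2 / 4.9 | 4.7 / 4.7 / 4.6 |
| 40% vs 60% | 0.06 / 0.10 / 0.16 | 5.7 / 8.0 / 13.9 | 5.6 / 7.0 / 12.5 | 5.3 / 5.1 / 5.1 | 5.1 / 4.7 / 5.1 |
| 30% vs 60% | 0.09 / 0.15 / 0.24 | 8.1 / 12.4 / 24.5 | 8.0 / 12.1 / 24.2 | 5.0 / 4.4 / 5.2 | 5.8 / 4.7 / 5.2 |

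The simulation error at a true 5% is √(0.05 × 0.95 / 3000) = 0.4 points. The adjusted comparison (a rank regression including the factor) and the randomised contrast stay near 5% throughout. The unadjusted comparison does so only when the imbalance or the effect is small. In the last row at 0.8 SD, the three-group test rejects in 24.2% of runs while test versus control rejects in 5.2%, so the former cannot stand in for the latter.

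**The case against.** Several counter-arguments have force.

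- **The primary contrast is randomised.** Correct; the point does not touch it.
- **The trial is exploratory (section 4), and 9.2 puts description first and treats inference as reference only.** This lowers the weight of any P value. It does not help with the bias, because an unadjusted descriptive difference is confounded in the same way.
- **Eligibility already narrows the groups.** Sections 5.1 and 5.2 restrict all groups to singletons, 37 to 42 weeks and 2500 to 4000 g, and exclude assisted reproduction, gestational diabetes and serious maternal disease. This stands: birth and maternal-health differences are limited, leaving mainly delivery mode, family background and centre.
- **The no-difference null is not realistic.** Section 2.1 itself describes breastfed and formula-fed flora as different. The rejection rates above therefore show the mechanism only; the bias in the estimated difference is the relevant quantity.
- **The breastfed group may serve only as a shared reference.** The study cited in 6.5.2 found test flora nearer than control flora to breastfed flora. Randomisation balances the two formula groups set against that reference. Confounding can still shift the reference itself, and it affects any direct formula-minus-breastfed difference read as an effect of feeding.
- **A separate analysis plan may add adjustment.** Possible, but the protocol does name an unadjusted method for the flora comparison.

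A reader might go further and infer that growth, cognition and immune results will be confounded by the same tests. The protocol does not support that: the named tests cover flora only, and the method for the secondary endpoints is left open.

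**Conclusion.** The point holds for flora comparisons that involve the breastfed group, and only for those. The protocol forms this group by choice, fixes unadjusted tests for it, and leaves recorded confounders out of every group comparison. An adjusted estimate from available data would be better than the stated method.

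The size is unknown. The 0.10 SD figure rests on an assumed 20-point imbalance and an assumed 0.5 SD effect; the assumed range above runs from 0.03 to 0.24 SD. A reader might infer a large false-positive rate: assumed total biases of 0.20 and 0.30 SD at 64 per group would give 20.5% and about 40% rejection. The arithmetic is right, but nothing in the protocol supports biases of that size, and the rates presuppose that breastfed and formula-fed flora do not differ. They should not be quoted as the expected error of this trial.

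This is an improvement that should be made to a supporting comparison. It is not a defect of the randomised result.

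**What to change.** Amend section 9.7.2 for formula-versus-breastfed flora comparisons:

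- **Alpha diversity:** add a covariate-adjusted difference with 95% CI, for example from a regression on delivery mode, sex, birth weight, parental education and centre. These are settled before or apart from the feeding received, so adjusting for them should not remove a feeding effect.
- **Beta diversity:** add a covariate-adjusted distance-based test with the same factors. A regression difference does not fit the heatmap, PCA or LEfSe outputs; leave those as descriptive or supportive.
- **Label** these comparisons observational, and keep the unadjusted rank tests as supportive.
- **Tabulate** delivery mode, parental education, birth weight, sex and centre by group, extending the summary in 9.5.
- **Test versus control:** state that it is reported as its own two-group comparison and not inferred from the three-group Kruskal-Wallis test. The two-group Wilcoxon already named can serve, so this only makes the intention explicit.

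The cost is some wording and slightly more analysis. Delivery mode and parental education come from Visit 1; birth weight, sex and centre are available, so no new visit or sample is needed. Adjustment covers only measured factors, so residual confounding must still be stated with the results.
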